4 DATA SOURCE

All data for this study will be collected via online REDCap surveys. *Table 1* includes a list of all study variables, which aim they are associated with, and which tool will be used for assessment.

Table 1: MHAPPS Trial Variables & Other Data Elements

Variables			
Outcomes	Tool	Aim Collected	Source
Loneliness	NIH Toolbox – Social Relationship Scales - Loneliness Scale	Aim 1	REDCap
Suicidal ideation & behavior	C-SSRS Screener	Aim 1	REDCap
Recent suicide attempts, suicide completion, & self-harm; lethal means	6-Months Suicide Attempts Survey	Aim 1	REDCap
Perceived Burdensomeness; Thwarted Belongingness	INQ-15	Aim 1	REDCap
Stress	NIH Tool Box – Perceived Stress 10	Aim 1	REDCap
Alcohol and Illicit drug use	Youth Risk Behavior Survey Questions	Aim 2	REDCap
Depression	PHQ-9	Aim 1	REDCap
Anxiety	GAD-7	Aim 1	REDCap
Uptake of outpatient mental health treatment	n/a	Aim 2	REDCap
Exposure (Baseline)	Tool	Aim Collected	Source
Age in years, age category (adult/peds)	Baseline Survey	Aim 1	REDCap
Sex	Baseline Survey	Aim 1	REDCap
Race and ethnicity	Baseline Survey	Aim 1	REDCap

Address including Zip code of residence (urban/rural)	Baseline Survey	Aim 1	REDCap
County of residence (urban/rural)	Baseline Survey	Aim 1	REDCap
Gender identity & sexuality	Baseline Survey	Aim 2	REDCap
Religion	Baseline Survey	Aim 2	REDCap
Occupation	Baseline Survey	Aim 1	REDCap
Education	Baseline Survey	Aim 1	REDCap
Living Situation (permanent, temporary)	Baseline Survey	Aim 1	REDCap
Number of People at Home	Baseline Survey	Aim 1	REDCap
Perceived Risk for COVID-19	Baseline Survey	Aim 1	REDCap
Masking Practices	Baseline Survey	Aim 1	REDCap
Social Distancing Practices	Baseline Survey	Aim 1	REDCap
Domestic Violence	Baseline Survey	Aim 2	REDCap
Local COVID-19 Prevalence			CDC or Idaho Department of Health & Welfare Prevalence Data
Process Variables		Source	
Aim 1 proportion of eligible participants completing survey			REDCap
Aim 2 proportion of eligible participants enrolled			REDCap
Participant feedback on phone call (CC+ arm only)			REDCap
Participant feedback on content and timing of caring messages			REDCap
“Dose” of follow-up contact: timing, type (phone vs text), and			Mosio

number of attempted and successful contacts from the Hotline		
“Dose” of Caring Contact text messages: date/time of each text message sent (* 11 text messages)		Mosio
Other Variables	Tool	Source
Does cell phone on record belong exclusively to study participant or is it shared?	Baseline Survey	REDCap
Alternative modes of contact	Contact Form	REDCap
Death		State Vital Records

4.1 Data Management

This study will employ a comprehensive data management plan. The results from the screening and baseline questionnaires (as well as informed consent documents) will be directly entered in REDCap. Participants will be assigned a unique identifier; Aim 2 participants will be randomly assigned to one of the two intervention arms during the informed consent process just prior to study enrollment. Follow-up specialists at the Hotline will record any attempt at contact or successful contact made. The statistics team will compile data for each participant from REDCap on a routine basis for reports and to build and maintain a complete dataset.

The University of Washington Institute of Translational Health Sciences (ITHS) hosts REDCap, a secure, HIPAA-compliant web application, which will be used for building and managing online surveys and databases for this research. ITHS provides REDCap support and an array of research data curation and storage support. Other databases (such as Access, Excel) may be used for study management purposes; all such data will be kept on secured, password-protected computers.

5 ANALYSIS SETS/POPULATIONS/SUBGROUPS

We plan to survey up to 4,000 participants to address Aim 1. The total sample size for the Aim 2 trial is 660 participants, selected as a subset of those who complete the Aim 1 survey. For each stratum (patients, providers/staff), a sample of 330 participants (165 in each arm) allows 80% power to detect a difference of 5 units in the primary outcome (loneliness) if a minimum of 70% of participants are retained through study completion.

5.1 Inclusion & Exclusion Criteria: Aim 1

Provider & Employee Inclusion Criteria

- Provider or Employee at St. Luke's Health System
- Adults ≥ 18 years of age
- Proficient in spoken and written English language

Provider & Employee Exclusion Criteria

- Individuals who are unable or unwilling to provide informed consent to participate
- Individuals who are study staff for this study or the SPARC Trial
- Individuals who are participants in the SPARC Trial

Patient Inclusion Criteria

- Patient at a SLHS ED or primary care study site
- Current MyChart account user
- Adults ≥ 18 years of age
- Minors 12-17 years of age
- Proficient in spoken and written English language

Patient Exclusion Criteria

- Individuals who are unable or unwilling to provide informed consent to participate.
- Individuals who are participants in the SPARC Trial

5.2 Inclusion & Exclusion Criteria: Aim 2

Provider & Employee Inclusion Criteria

- Moderate or high score for loneliness, suicide ideation, psychological stress, anxiety, or depression:
 - NIH Toolkit Loneliness raw score of 13 or greater; or
 - C-SSRS score of 3 or greater; or
 - NIH Toolkit Perceived Stress raw score of 31 or greater for adults; or
 - GAD7 score of 11 or greater; or
 - PHQ9 score of 10 or greater
- Access to a phone for the duration of the study with the ability to receive text messages and phone calls

Provider & Employee Exclusion Criteria

- Individuals who are unable or unwilling to provide informed consent to participate
- Individuals who are study staff for this study or the SPARC Trial

Patient Inclusion Criteria

- Moderate or high score for loneliness, suicide ideation, psychological stress, anxiety, or depression:
 - NIH Toolkit Loneliness raw score of 13 or greater for adults and 16 or greater for adolescents; or

- C-SSRS score of 3 or greater; or
- NIH Toolkit Perceived Stress raw score of 31 or greater for adults or greater than 33 for adolescents; or
- GAD7 score of 11 or greater; or
- PHQ9 score of 10 or greater
 - *Note: validated youth versions of the NIH Toolkit assessments (loneliness and perceived stress), and PHQ-A tools will be used for adolescents; the C-SSRS and GAD7 tools are validated for use with both adults and adolescents*
- Access to a phone for the duration of the study with the ability to receive text messages and phone calls

Patient Exclusion Criteria

- Patients who are unable or unwilling to provide informed consent/assent to participate (or whose legally authorized representative is unable or unwilling to provide consent in the case of adolescents). Examples may include but are not limited to patients who present with acute or chronic cognitive impairment that would preclude their ability to consent (i.e. acute psychosis, intoxication, or intellectual disability).

5.3 Analysis Populations

1. Aim 1: All participants who complete the survey will be included in the data tabulations.
2. Aim 2:
 - a. **Intention to Treat (ITT) Population:** Data for all participants that complete study enrollment and the baseline survey will be included in this dataset. The primary and secondary endpoints will be evaluated in this group.
 - b. **Safety Analysis Population:** All safety analysis will include all participants who completed study enrollment and the baseline survey (equivalent to the ITT population).
 - c. **Per-Protocol Analysis Population:** The per-protocol analyses will include the subset of participants who were retained for the duration of the study and completed the assigned intervention as outlined in protocol section 9.
 - d. **Additional Populations:** Additional populations may be used to complete sensitivity analyses, for example, where missing data have been imputed using different techniques.

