5.2 Recruitment Strategy

A random selection of MyChart users who have attended a primary care visit at SLHS within the past 12 months will be recruited for the Aim 1 survey through a message including a REDCap survey link sent to their MyChart account or email. A comprehensive list of providers and employees and their email addresses will be obtained from a contact in the SLHS Human Resources Department, Digital and Analytics, or another appropriate department and a random sample of providers and employees will be selected using appropriate software. Those randomly selected will be recruited for the Aim 1 survey through an email message including a REDCap survey link. The Aim 1 survey will include an option to opt out of being contacted by study staff for participation in a follow-up study if they are potentially eligible. Participants who indicate interest in the follow-up study who also report elevated mental distress will be the source population for Aim 2. Recruitment for Aim 2 will involve study staff contacting potential participants to describe the Aim 2 clinical trial, conduct informed consent, and enroll interested patients into the trial. Recruitment-related emails will be either automatically sent via REDCap, sent from the [contact] email address, sent from the PI, delegated study staff, or sent via MyChart. In the event that there are more eligible and interested potential participants than available space in the trial, potential participants will be invited to participate in the order in which they completed the Aim 1 Survey.

For Aim 1, informed consent and study enrollment will be completed by the participant electronically through REDCap, with study staff available by phone or email to answer any questions. For Aim 2, informed consent and study enrollment will be conducted by trained study staff, typically a Research Coordinator over the phone or via video chat. All staff conducting informed consent and study enrollment will be trained in human subjects' protection and study procedures and will be delegated to do so by the study PI.

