5.4 Populations for Analyses

Analyses will be completed using the following populations:

1. **Intention to Treat (ITT) Analytic Population:** Data for all participants that complete study enrollment will be included in this dataset.
2. **Safety Analysis Population:** The dataset shared with the Data & Safety Monitoring Board for safety analysis will include data for all participants who completed study enrollment (e.g., the ITT Analytic Population Dataset).
3. **Per-Protocol Analysis Population:** Data for a subset of participants who were retained for the full study, were sent all 11 caring text messages, and received a phone call if randomized to the CC+ intervention (as outlined in protocol section 9) will be included in this dataset.
4. **Additional populations:** Additional datasets may be developed to complete sensitivity analyses, for example, where missing data have been imputed using different techniques.

6. Study Procedures

Aim 1: Cross Sectional Survey (Email REDCap survey link for providers and staff; send REDCap survey link via MyChart or email for patients)

- Aim 1 study enrollment and informed consent
- Aim 1 Survey
 - Demographics questions
 - C-SSRS (suicide risk)
 - NIH Toolbox Social Relationship Scales (loneliness, stress)
 - INQ (defeat, entrapment, perceived burdensomeness, and thwarted belongingness)
 - PHQ-9 (depression)
 - GAD-7 (anxiety)
 - COVID-19 beliefs and practices survey (brief)

Aim 2: Baseline / Enrollment (Subset of Aim 1 participants; see below)

- Aim 2 study enrollment and informed consent (phone call with Research Coordinator or study staff to complete via REDCap)
- Aim 2 Baseline assessments (Email or text REDCap survey link)
 - Baseline survey (Socio-economic status, gender identity, sexuality, religion, and alcohol and illicit drug use)
 - Expanded COVID-19 beliefs and practices survey (additional questions related to impact of COVID-19 on the individual, and his/her/their family, friends, and community)
 - Contact Sheet to collect alternative forms of contact for study participant

Aim 2: Caring Contacts Interventions (see description of interventions in section 9)

- **CC+:** 1 call, within 2 weeks of enrollment, and 11 caring text messages, sent from Hotline

follow-up specialists according to a standardized schedule over a 6-month period

- **CC:** 11 personalized caring text messages sent from Hotline follow-up specialists according to a standardized schedule over a 6-month period

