Variables will be measured through the Aim 1 survey or Aim 2 Baseline survey and reported using descriptive statistics. Potential effect modifiers will be assessed and include age, sex, gender identity, sexuality, race/ethnicity, religion, employment, urban/rural residence, drug/alcohol use, suicidal ideation at baseline, baseline depression score, baseline anxiety score, baseline stress score, baseline quality of life, measures of socioeconomic status and/or other variables related to the specified outcomes of interest. Data will be analyzed according to both an intention to treat protocol and per protocol received. Please see section 5.4 *Populations for Analyses* for further detail.

This study will report the distribution of key variables to facilitate assessment of the study's internal and external validity. At a minimum, this study will report the distribution of key variables within the analytic population (key variables are defined as those that are included in the causal diagram at the beginning of the *Research Design* section of this Research Plan). Missing data will be assessed on a regular basis through routine data reports. These reports will allow the investigators to assess the cause of missing or anomalous entries, and address these if possible. If missing values cannot be retrieved, the reason for the missingness will be recorded in data comments available through REDCap. Study staff will record the reason for any participant drop-out during the 6 months of follow-up.

[13.2 Power & Sample Size for Aim 2](#)

The total sample size for the aim 2 trial is 660 participants. For each stratum (patients, providers/staff), a sample of 330 subjects (165 in each arm) allows 80% power to detect a difference of 5 units in the primary outcome (loneliness) if a minimum of 70% of participants are retained through study completion.

[13.3 Duplicate Surveys](#)

A data cleaning step will be included to identify surveys completed twice by the same individual. This may occur, for example, when an individual is both a provider/staff person and a patient at SLHS. If duplicate surveys are identified, the first will be retained, and the second will be excluded from the research.

[13.4 Missing Data](#)

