Study staff (including anyone involved in enrollment and informed consent or delivery of the follow-up intervention or outcome measurements, and/or having access to patient-level data) will be trained on the protection of human subjects and HIPAA, with a focus on topics relevant to confidentiality. SLHS staff will assist participants in completing Aim 2 informed consent, and REDCap survey links will be sent out via text, email, or MyChart. Study staff at SLHS, University of Washington and the Hotline will have access to protected health information (PHI).

The study is designed to be low burden in terms of participants' time. The initial survey (Aim 1) will consist of up to 50 multiple choice questions. Those participants who enroll in the comparative effectiveness trial (Aim 2) will complete a baseline survey (up to 50 questions), receive 11 caring text messages over a 6-month period, and depending on intervention arm, may also receive an introductory

phone call. Aim 2 study participants will complete an outcomes assessment survey online, which will consist of up to 50 questions. Participants will be reimbursed for their time.

Participants will be under no duress or pressure to participate in or complete this study.

- *Patient Participants.* Participating in this study will not impact the care they receive, and this will be clearly communicated to participants as part of the informed consent process.
- *Provider/Staff Participants.* Participating in this study will not impact their employment, and information received in this study will not be shared outside of the study staff. This will be clearly communicated to participants as part of the informed consent process.

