16.2.2 Involvement of Human Subjects

Suicide constitutes a significant public health concern and is a leading cause of death in the United States.²³ However, little is known about health system level interventions to prevent suicide among civilians, or adolescents.¹¹⁷ Additionally, mental distress related to COVID-19 is a critically important but poorly understood aspect of the global pandemic.^{25,28} This study will estimate the prevalence of several measures of mental distress in key populations and compare the effectiveness of two versions of the evidence-based Caring Contacts model. The proposed research design is a randomized clinical trial, and all study participants will receive an active evidence-based intervention. No one will receive a “placebo” or “null” treatment.

Participation in this research involves the following:

Aim 1: Survey

- Complete an online survey (10 minutes)

Aim 2: Comparative Effectiveness Trial

- Baseline (Month 0)
 - Complete study enrollment and informed consent (30 minutes)
 - Complete baseline survey (20 minutes)
- Months 0-6
 - Receive Caring Contacts intervention (6 months)
 - 1 introductory phone call (one intervention arm only) (20 minutes)
 - 11 caring text messages (both intervention arms)
- Month 6
 - Complete online outcome assessment survey at 6 months (20 minutes)

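### SAP 5.3 makes completion of the baseline survey a condition of the ITT and safety sets; Protocol 5.4 does not, and on the more natural reading randomised participants can be dropped

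*SAP*

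**What the plan says.** Protocol 5.4 defines the ITT population thus: "Data for all participants that complete study enrollment will be included in this dataset". The dataset that goes to the DSMB for safety is the same one.

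SAP 5.3, under Aim 2, reads: "Data for all participants that complete study enrollment and the baseline survey will be included in this dataset". It adds that the primary and secondary endpoints are evaluated in that group, and it repeats the survey condition for the safety population.

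On timing, Protocol 4.2 and 12.2 randomise straight after consent and enrolment. SAP 4.1 randomises during consent, shortly before enrolment. Protocol 5.2 describes Aim 2 enrolment as a staff contact: "informed consent and study enrollment will be conducted by trained study staff, typically a Research Coordinator over the phone or via video chat". Protocol 6 lists the Aim 2 baseline assessments as a REDCap link sent by email or text, and 16.2.2 lists the survey as its own 20-minute step.

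**The concern.** Protocol and SAP define the primary analysis set differently. If the SAP clause means the Aim 2 survey, and nothing requires that survey to be finished before assignment, inclusion depends on something a participant does or fails to do after being randomised. Protocol 4.3 says participants cannot be masked, so completion could differ by arm.

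Anyone dropped this way is outside the primary model, the hot-deck imputation (SAP 7.3), the 10% missing-data trigger and the tipping-point analysis (SAP 7.4). The plan's own missing-data safeguards would not register the loss. The effect on safety is smaller: these people would be absent from the SAP safety tables, but the protocol's DSMB dataset covers everyone enrolled.

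**Working it through.** **1. Which survey is meant?** Three readings are possible.

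- *Aim 2 survey, separate from enrolment.* The clause sits under Aim 2, and item 1 of the same SAP list calls the Aim 1 instrument simply the survey. The protocol uses the baseline name only for the Aim 2 instrument (6, Table 1, Table 2, 13.1, 15.1, 16.2.2); in 13.1 the two are named apart: "Variables will be measured through the Aim 1 survey or Aim 2 Baseline survey". Assignment is tied to consent and enrolment, not to the survey. Randomised people can then be dropped.
- *Aim 2 survey as part of enrolment.* Protocol 6 puts both under one heading, 5.3 hands out the contact sheet at enrolment, and Table 1 lists the survey row above randomisation in the same 0-week column. If the survey had to be finished first, nobody randomised would be lost. No passage says so.
- *Aim 1 survey.* SAP Table 1 gives Baseline Survey as the tool for 12 rows marked Aim 1 and 3 marked Aim 2. Every trial participant has already completed the Aim 1 survey (SAP 5), so the clause would exclude nobody.

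**2. Does the primary analysis need the clause?** No. Loneliness is collected in the Aim 1 and outcome surveys (Protocol Table 2). The model adjusts for the baseline score (SAP 7.2.1), and the hot-deck cells use arm, baseline loneliness tertile and population (SAP 7.3). None of these comes from the Aim 2 survey.

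**3. Counts.** No non-completion rate is given. 660 × 0.01 = 6.6; 660 × 0.05 = 33; 660 × 0.10 = 66. Per arm per stratum: 165 × 0.05 = 8.25 and 165 × 0.10 = 16.5.

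**4. SD for illustration.** The stated 80% power cannot be reproduced because no SD is given. Solving back from 5 units, two-sided 0.05 and 165 × 0.70 = 115.5 retained per arm: SD = 5 / (2.802 × √(2/115.5)) = 13.56. At that SD, with 70% of those left retained, excluding 5% or 10% lowers power to about 78% or 76%.

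**5. Bias under assumed skipping.** If a fraction p of an arm is dropped and differs by D units from those kept, the kept mean is off by p × D. The unadjusted bias is the difference between arms:

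- 10% vs 5%, D = 5: (0.10 − 0.05) × 5 = 0.25
- 15% vs 5%, D = 10: (0.15 − 0.05) × 10 = 1.00

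With an assumed baseline–outcome correlation r = 0.5, adjustment multiplies this by about 1 − r² = 0.75, giving 0.19 and 0.75. Simulation, with skipping logistic in the 6-month outcome and no true effect, gave 0.18 and 0.76: 0.18/5 = 4% and 0.76/5 = 15% of the planning difference. With equal skip rates and equal gaps in both arms the bias was about zero.

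**6. Type I error.** Adjusted SE after the modelled exclusions = 13.56 × √0.75 × √(1/n₁ + 1/n₂).

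- 10% vs 5%: n = 103.95 and 109.73, SE = 1.61
- 15% vs 5%: n = 98.18 and 109.73, SE = 1.63

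Type I error = Φ(−1.96 + b/SE) + Φ(−1.96 − b/SE), which is about 5.1% for b = 0.18 and 7.5% for b = 0.76.

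**7. What deleting the clause recovers.** Simulated bias left under the SAP 7.3 hot deck, with everyone else 70% retained (the first row is with the clause kept):

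| | 10% vs 5%, gap 5 | 15% vs 5%, gap 10 |
|---|---|---|
| Clause kept | 0.18 | 0.77 |
| Deleted, non-completers 70% retained | 0.00 | 0.00 |
| Deleted, 40% retained | 0.07 | 0.30 |
| Deleted, none retained | 0.19 | 0.82 |

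Repeat runs agreed to within about 0.03. Deletion helps only as far as non-completers supply 6-month data. If none do, the bias is no smaller, but they count as missing and enter the SAP 7.4 sensitivity analyses.

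**The case against.** The best case for the plan is that nobody randomised is lost on two of the three readings, and that there is more support for those readings than the section headings suggest. The payment list in Protocol 16.7.1 has no separate item for the Aim 2 baseline survey, which fits treating it as part of enrolment. Protocol 12.2 and SAP 4.1 both mention baseline questionnaires before they mention assignment. The disputed words are in the SAP, whose own Table 1 uses the baseline label mostly for Aim 1 variables.

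Harm is not demonstrated either. Bias needs skipping that differs by arm in how often it happens or how it relates to outcome. The documents give no skip rate and do not say when participants learn their arm. Deletion also brings no gain if non-completers never return.

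Much of this stands: the alternative readings are open, and the bias figures are illustrations only. It does not remove the point. None of the cited passages makes the survey a condition of randomisation, and the two definitions still differ. On the readings that exclude nobody the clause does no work, so removing it is correct or harmless on all three.

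**Conclusion.** The concern holds. The conflict between Protocol 5.4 and SAP 5.3 is plain from the text. That it permits exclusion after randomisation rests on the more natural reading, not on an explicit statement, so confidence in that step is medium.

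Whether bias would occur, and its size and direction, cannot be determined from the documents. The range of 0.18 to 0.76 units depends on assumed skip rates, assumed outcome gaps, r = 0.5 and a back-solved SD. The case rests on the definitions, not on that range. This should be fixed: it concerns the set in which the primary endpoint is evaluated, and the clause serves no purpose there.

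A related gap adds to it. Under SAP 4.1 assignment comes before enrolment, so even the requirement of completed enrolment could omit someone already assigned.

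**What to change.** - In SAP 5.3, delete the baseline-survey condition from both definitions. Define the ITT and safety sets as all randomised participants, analysed as assigned, with baseline scale scores taken from the Aim 1 survey.
- Reconcile SAP 4.1 with Protocol 4.2 and 12.2 on the order of enrolment and assignment. This should go with the first change: under the SAP 4.1 order, all randomised could include someone who never finished consent.
- If the Aim 2 survey is meant to be completed before randomisation, say so in Protocol 4.2 and SAP 4.1. All randomised then gives the same set without the clause.

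The cost is wording in the SAP, plus a protocol edit if the survey is meant as a gate; the protocol's compliance statement requires IRB approval for amendments to the protocol or supporting documents. Analyses that use Aim 2 baseline items (change in alcohol and drug use, the gender identity and sexuality subgroups, religion as an effect modifier) will have some missing baseline values, to be handled within those analyses. If the clause meant the Aim 1 survey, deleting it changes nothing.
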